We hypothesize: 1) Subjects will show improved mobility after 10 weeks of twice weekly karate classes, as measured by change in Timed Up & Go (TUG)¹; 2) The majority of subjects will report a positive change from baseline in their overall wellbeing, as measured by a response of "very much improved", "much improved" or "minimally improved" on the Patient Global Impression of Change Scale (PGIC)² following 10 weeks of classes; 3) Feasibility will be high, as measured by $\geq 75\%$ attendance rate and a response of "yes" to either "Would you recommend this program to someone else with PD?" or "If available, would you continue to participate in this or a similar karate class?" Exploratory outcomes will include measures of gait and balance, including change in functional reach test (FRT)³ and change in Tinetti Mobility Test (TMT)^{4,5}, along with change in anxiety and depression, as measured by the Hospital Anxiety and Depression Scale (HADS), and measures of attention such as the Symbol Digit Modalities Test (SDMT) and the Digit Span Test (DST)⁶

I.b. Background

Parkinson's Disease, the second most common neurodegenerative condition⁷ presents a significant health concern and the progressive, incurable course of the disease impacts functional abilities of the patient and quality of life for both the patient and caregivers. Exercise is an established supplement to pharmacologic PD treatment and various modalities have demonstrated benefits in gait, balance, PD symptoms, and quality of life measurements.^{8,9,10} Research has encompassed many forms of exercise, including aerobic activities and mindfulness-based practices. Vigorous, aerobic activity has been repeatedly shown to have disease-modifying effects ranging from quality of life to overall cognitive and physical improvement.¹⁰ Mindfulness-based practices, such as tai chi, have seen a recent surge in interest and an overall beneficial effect for participants.^{11,12} A notable trial compared resistance training,

stretching and tai chi interventions among Parkinson's patients and while both the resistance and tai chi arms showed improvements on multiple measures of physical ability, tai chi demonstrated a significantly greater impact in measures of balance and postural stability.¹³ Furthermore, resistance training and tai chi were both correlated with improved patient-reported outcomes and participants in the tai chi group who reported benefits were more likely to continue their exercise programs.¹⁴

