The PI and research team will collaborate with a professor of Cinema and Television Arts from Columbia College Chicago, IL to develop a documentary to educate others about karate as an interactive form of exercise and its potential benefits on the symptoms and quality of life of people with PD. To capture the groups' journey over 10-weeks, portions of the pre-intervention focus group, the karate classes, and the post-intervention focus group will be videotaped. For a more in-depth look, two to three subjects will be followed during the entire study and interviewed to provide a personal narrative of their experiences with the karate classes and living with PD. The interviews will be videotaped.

We will recruit 30 individuals with PD diagnosed by a neurologist, ages 30-90, living in Chicago, and with Hoehn & Yahr (HY) stage 1 (unilateral symptoms, no balance issues), stage 2 (bilateral symptoms, no balance issues), or stage 3 (bilateral symptoms, some postural or balance involvement). Subjects will be assigned to one of two cohorts of 15 subjects each, based on dojo location and class schedule. For example, one cohort may take classes Tuesday and Thursday nights at the Wilmette dojo, and the second cohort may take classes Wednesday and Saturday mornings at the Glenview dojo, however class times and locations are to be determined.

II. Characteristics of the Research Population

II.a. Number of Subjects

Total Number of Subjects: 30

This is a pilot study; our power analysis (see table below) is based on the TUG, with the following assumptions: mean TUG score for individuals with PD is 14.8 seconds with standard deviation of 5.8 seconds, alpha of 0.05, and correlation between baseline and follow-up assessments of 0.5. We calculated sample sizes necessary with various minimum clinically important difference values for the TUG, which ranges from 2 seconds to 5 seconds in various studies^{1,18}, and varying for power between 80-90%. With a sample size of 30, we will have 80% power to detect a change of 3 seconds in the TUG, and will be more than 90% powered to detect a change of 4 seconds or greater.

| Baseline mean TUG | Baseline SD TUG | Min. clin. Important difference | Correlation b/w baseline, follow-up | Power | Sample size |
|-------------------|-----------------|---------------------------------|-------------------------------------|-----------|-------------|
| 14.8s | 5.8 | 2s | 0.5 | .9 | 89 |
| | | | 0.5 | .8 | 67 |

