- *Timed Up and Go (TUG):* A well-validated, brief measure of mobility. Administered by a study team member with a stopwatch who has previously measured out the distance between a standard arm chair and a taped line on the ground 10 feet (3 meters) away, subjects sit in a standard arm chair and are instructed that when the team member says "Go", they should stand up from the chair, walk at their normal pace to the line, turn, walk back to their chair at a normal pace, and sit down again. The study team member will record the TUG results in seconds using a stopwatch. This is a recommended test of balance in PD.²¹
- *Functional Reach Test (FRT):* This brief, valid, reliable, and practical assessment of balance involves a yardstick being mounted on a wall at shoulder height. The subject is asked to stand next to the yardstick, extend the arm closest to the wall at 90 degrees of shoulder flexion, and the distance is recorded. The subject is then asked to reach as far as he or she can forward without taking a step, and the distance is recorded again. The difference between start and end position is the reach distance.³ This is a recommended test of balance in PD.²¹
- *Tinetti Mobility Test (TMT):* This balance scale has strong psychometric properties and consists of 2 subscales: balance tests (9 items, scored from 0-16) and gait tests (7 items, scored from 0-12), where higher scores reflect better performance.⁵ This meets criteria for a "suggested" scale in PD. This is a recommended test of balance in PD.²¹
- *Hospital Anxiety and Depression Scale (HADS):* Brief, 14-item highly validated scale for measuring anxiety (7 items) and depression (7 items), where scores of >8 for either anxiety or depression indicate probable symptoms.⁶ The HADS was selected due to its use in prior peer mentoring studies and strong psychometric profile

- *Modified Unified Parkinson's Disease Rating Scale (UPDRS)*: A shortened version of the UPDRS motor subscale will be conducted by the PI or study staff, assessing only rigidity, resting tremor, and bradykinesia in all four extremities and the head/neck, as well as postural stability, in order to determine the subject's HY stage.

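### The TUG procedure describes one timed circuit with no practice walk, repeat or scoring rule, so test familiarity can bias the uncontrolled pre/post change and trial error costs some precision

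*Combined protocol and SAP*

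**What the plan says.** The only TUG procedure is the entry in the Assessments list of Section III. Subjects are told that "they should stand up from the chair, walk at their normal pace to the line, turn, walk back to their chair at a normal pace". Sitting down ends the circuit. The entry continues: "The study team member will record the TUG results in seconds using a stopwatch". It gives no number of trials, no practice walk, and no choice between a single, mean or best time.

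The visit descriptions in Section III (Pre-Intervention Focus Group and Post-intervention focus group) list the TUG among the tests and add nothing on how it is run. Section III.b tests the change in TUG by a paired t-test or a Wilcoxon signed-rank test. It does not define the value that enters the test.

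The TUG is the measure named in hypothesis 1, and in Section II.a "our power analysis (see table below) is based on the TUG". Section I.c describes a single open-label intervention and no control group.

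**The concern.** Two separate mechanisms are at work, and they have different consequences.

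- **Learning.** If staff follow the text literally, the baseline time is a subject's first attempt in the study and the later time is a second attempt. Any gain from knowing the task points the same way as the hypothesised benefit. With no control group, the analysis cannot separate the two.
- **Trial-to-trial error.** Back-to-back walks by the same person differ. With one walk per visit, all of that variation enters the change score. This lowers power but leaves the mean change unbiased.

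The missing scoring rule adds a smaller risk. Staff could time one walk at one visit and several at the other, or keep the best of several, and still comply with the text.

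**Working it through.** **Inputs from Section II.a.** "mean TUG score for individuals with PD is 14.8 seconds with standard deviation of 5.8 seconds". The plan also sets a pre/post correlation of 0.5, alpha 0.05, N = 30 and a target change of 3 s. The sidedness of alpha is not stated. The documents give no within-session trial SD and no learning effect, so both are assumed over a range below.

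**Step 1: reproduce the plan's figure.**
- SD of change = 5.8 × √(2 × (1 − 0.5)) = 5.8 s, variance 33.64.
- With two-sided alpha 0.05 and the normal approximation, n = (5.8 × (1.960 + 0.842) / 3)² = 29.34, rounded up to 30. The same formula gives all eight entries of the table. A one-sided test would give 24 here, so the table is two-sided.
- Power at 30 pairs for 3 s is 80.9% by the normal approximation and 78.2% by the exact paired t-test (noncentrality 3 / (5.8/√30) = 2.83, 29 degrees of freedom). The exact test needs 32 pairs for 80%.

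**Step 2: effect of averaging two timed walks.** Assume that 5.8 s and r = 0.5 describe single trials, so that single-trial error with SD s is already inside the 33.64. One trial contributes 2s² to the variance of change and the mean of two contributes s². The variance becomes 33.64 − s².

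| Assumed trial SD (s) | SD of change, mean of two (s) | Exact power, 3 s, 30 pairs |
|---|---|---|
| one trial only | 5.80 | 78.2% |
| 0.5 | 5.78 | 78.5% |
| 1.0 | 5.71 | 79.4% |
| 1.5 | 5.60 | 80.9% |
| 2.0 | 5.44 | 83.1% |

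The gain is 0.3 to 4.9 percentage points.

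**Step 3: effect of learning.** Suppose karate has no effect, and familiarity alone shortens the second time by L seconds on average, with SD of change 5.8 s. The chance of a two-sided p < 0.05 at 30 pairs is the exact t-test power at L.

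| Assumed learning gain L (s) | Share of the 3 s target | Chance of a significant result |
|---|---|---|
| 0 | 0 | 5.0% |
| 0.5 | 17% | 7.4% |
| 1.0 | 33% | 15.0% |
| 1.5 | 50% | 27.8% |

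For scale, the smallest observed mean change that reaches p < 0.05 is 2.045 × 5.8/√30 = 2.17 s.

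**The case against.** The strongest reply is that the text is silent, not restrictive. Describing a circuit once is normal in a short instrument summary, and the Functional Reach Test entry is written the same way. A reader might infer that the protocol prescribes exactly one trial and rules out practice. It does not say so. What stands is that nothing in the documents provides for practice, repeats or a scoring rule, and that literal compliance yields one unpractised walk.

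The second reply concerns the power gain. Section II.a does not say whether 5.8 s and r = 0.5 come from single or averaged trials. If they already reflect averaging, Step 2's gain does not follow, and averaging would only help to meet the planning assumptions. The correlation is also a planning value. Over 10 weeks the unshared variance includes real differences in response, fluctuation of the disease and permitted medication changes, so it cannot be read as measurement error. This stands, and it is why Step 2 is conditional.

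A reader might attribute half of the visit-specific variance (33.64 / 2 = 16.82) to trial error and so reach a power of 88.5%. That needs a back-to-back SD of √8.41 = 2.9 s, about 20% of a 14.8 s mean. Nothing in the documents supports a value that large.

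Finally, a practice walk cannot repair a single-arm, unblinded comparison. That is correct, but it limits the benefit of the change and is no reason against it.

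**Conclusion.** The point holds as a low-cost improvement. As described, the TUG measurement leaves first-exposure learning in the estimate of benefit and trial error in its spread. Learning is the more serious of the two because it acts as bias: an assumed gain of 0.5 to 1.5 s raises the chance of a false positive finding from 5% to between 7% and 28%. The precision gain from averaging is modest, from 78.2% to between 78.5% and 83.1%. It depends on two assumptions: a trial SD of 0.5 to 2 s, and planning values that describe single trials. Neither effect can be sized from the documents.

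Two stronger readings are not supported. A reader might infer that the sample size is wrong. The table reproduces exactly, the gap between 80.9% and 78.2% comes from the normal approximation, and the planning SD may already contain trial error. A reader might also call the TUG the declared primary endpoint. The documents give it that weight through hypothesis 1 and the power analysis but never use the word for it.

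**What to change.** In the TUG entry of Section III, state that at both visits each subject takes one untimed practice walk and then two timed walks under identical instructions. In Section III.b, state that the mean of the two timed walks is the TUG value in all analyses.

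The cost is two extra walks per visit. At the planning mean that is 2 × 14.8 = 29.6 s plus resets, or about one minute per subject per visit with the same staff and stopwatch. The downside is that the assessment block is planned at only 15 minutes, so the schedule should be checked.

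The change reduces first-attempt learning and noise. Expectation and other uncontrolled pre/post effects remain and should still be named as limitations. If the sponsor prefers a single timed walk, stating that explicitly for both visits would at least make the two measurements comparable.

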In the week prior to the 10th class, the study team will contact subjects to remind them of the date and time of the final class and the post-intervention focus group. The post-intervention assessment will consist of a repeated TUG, FRT, TMT, HADS, PDQ-8, SDMT, DST, brief question about falls in the past 10 weeks, and PGIC. Each subject will receive their initial response to the "What do you hope to achieve in this class?" prompt, and will be asked to reflect in a written, open-ended manner on whether they feel that they achieved their goal. In addition, subjects will indicate their response to the following questions regarding feasibility: "Would you recommend this program to someone else with PD?" and "If available, would you continue to participate in this or a similar karate class?"

Subjects will then participate in a focus group, similar to the pre-intervention focus group, in which they be asked to share and reflect on how the intervention affected their overall attitude towards exercise; how it affected their balance and falls; how it affected their mindfulness; any other positive or negative benefits; any impact on their care partner(s) (if applicable); and suggestions for changes to the intervention for the future. Depending on availability of space, the post-intervention focus group may take place at Rush University, or may take place immediately following the last class at the respective dojo.

Documentary

Portions of the focus groups and karate classes, and the entire in-depth interview will be videotaped by the Columbia filmmakers using personal equipment. Subjects may choose to not participate in the documentary project which means subjects will not participate in the in-depth video interviews, and they will not be included in individual or group video shots during the focus groups and karate classes. To ensure confidentiality, subjects will be placed in one of two groups, Group A or Group B, depending on whether they decide to participate in the documentary or not. Subjects who agree to be videotaped and possibly interviewed will be part of Group A while subjects who choose not to be videotaped or interviewed will be in Group B. Subjects may not switch groups after the study begins with the pre-intervention focus group. Participation in the karate classes and focus groups will not be affected if a subject does not wish to be videotaped or interviewed. Subjects will not be penalized if they decide to not take part in the documentary

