- *Patient Global Impression of Change (PGIC)*: This single-item rating scale administered only at the post-intervention assessment asks subjects to rate their overall response to the intervention using a 7-point rating scale, with the options of “very much improved”, “much improved”, “minimally improved”, “no change”, “minimally worse”, “much worse” and “very much worse”. Recommendations for assessing importance of this scale include reporting the percentages of subjects endorsing each of the 7 response options.
- *Parkinson's Disease Questionnaire- Short Form (PDQ-8)*: A validated and shortened version of the PDQ-39, with 8 items each representing one domain of the PDQ-39, also with a summary index score standardized to a scale of 0-100, with higher scores signifying worse quality of life; this scale is recommended for use in PD by the Movement Disorder Society.
- *Symbol Digit Modalities Test*: This uses a reference key while the examinee has 90 seconds to pair specific numbers with given geometric figures. Responses can be written or oral, and for either response mode, administration time is 5 minutes. The WPS AutoScore Test Form simplifies scoring. SDMT allows the opportunity to compare written and spoken responses from the same individual. The Manual provides separate norms for written and oral administrations of the test. Norms for adults are separated by age group and level of education.
- *Digit Span Test*: This tests the number of digits a person can absorb and recall in correct serial order after hearing them or seeing them. Here the person has to remember a small amount of information for a relatively short time, and the order of recall is important. To test the auditory digit span of a person, the administer says numbers slowly in one second intervals, in a monotone voice. For example, the administer will say 6-1-5-8 and have the person repeat it back in the order it was given or the reverse order. If the person is able to say a 4 digit sequence back correctly 75% of the time on the first try, it will be considered a short term memory of 4, and is the same for each higher digit. The average in our society for a seven-year old to adult is 7.

III.b. Data Analysis and Data Monitoring

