Oversight of the Data: Karate for PD will be maintained by the Principal Investigator. The Principal Investigator will review study procedures annually and report any concerns in the IRB continuation application. This is a Level I, Low, Minimal Risk study; therefore, there is minimal risk of unanticipated problems with the exception of breaches in confidentiality. The quantitative data for the study will be entered into a secured database using an electronic data capture program, Research Electronic Data Capture (REDCap).²² The database will be stored on a secure password-protected server and not on individual desktop computers. The code sheet will be password protected and the password will be updated annually. Breaches of confidentiality will be reported to the IRB immediately with the “Reportable Event/Unanticipated Problem Form.”

Data will be exported from REDCap in de-identified format for statistical analysis, with all PHI stripped from the dataset prior to analysis by statisticians. We will summarize categorical variables by

frequencies and percentages and will assess continuous variables for normality, summarized by mean/standard deviation, or median/interquartile range. We will report the basic descriptive statistics of the cohort, including baseline TUG, FRT, TMT, HADS, PDQ-8, SDMT, and DST, stratified by HY stage. We will report on attendance, defined as the percentage of classes attended, where 20 is the denominator. We will analyze the change in TUG, FRT, TMT, HADS, PDQ-8, SDMT, and DST, respectively, from pre- to post-intervention, using paired *t*-tests or nonparametric Wilcoxon sign rank tests, as appropriate, stratifying for HY stage. We will report on the percentage of subjects endorsing each of the 7 PGIC response options, stratifying for HY stage. We will report the descriptive statistics concerning whether subjects' individual predefined goal for the class was achieved (binary outcome), and will present de-identified qualitative comments noted in the feedback at the post-intervention assessment. We will report descriptive statistics on continued interest and likelihood of recommending the program to someone else with PD. After the 6-month follow-up call, we will analyze descriptive statistics on continued involvement in karate/martial arts, and will again report the percentage of subjects endorsing each PGIC response option.

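### The 10-week PGIC and the two acceptability questions have one collection point, at the end of the course, with no stated route for subjects who miss it and no stated denominator

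*Combined protocol and SAP*

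**What the plan says.** Hypothesis 2, in Section I, is about enrolled people in general: "The majority of subjects will report a positive change from baseline in their overall wellbeing", judged by any of the three improved categories of the PGIC after 10 weeks. Hypothesis 3 calls feasibility high if attendance is at least 75% and the subject answers 'yes' to either of two questions, on recommending the class or continuing it.

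Both sets of answers come from one session. The PGIC entry in the Section III assessment list reads "This single-item rating scale administered only at the post-intervention assessment asks subjects to rate their overall response to the intervention". The paragraph on the post-intervention focus group lists the PGIC among that session's measures and then adds the acceptability items: "In addition, subjects will indicate their response to the following questions regarding feasibility". The introduction to the assessment list places the closing assessments directly after the final class. The focus group may be held at the dojo following that class or at the university.

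For analysis, Section III.b says: "We will report on the percentage of subjects endorsing each of the 7 PGIC response options, stratifying for HY stage". It promises descriptive statistics on continued interest and on recommending the programme. It fixes a denominator for attendance (20 classes) but gives none for these percentages. The six-month phone call repeats the PGIC and asks about continued martial arts participation. The two acceptability questions are not listed for it.

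**The concern.** In a 10-week exercise pilot with feasibility as an explicit aim, stopping is itself information about benefit and acceptability. Someone who leaves because the class was too hard or unhelpful is plausibly less likely to rate themselves improved or to recommend it. A session held at the end of the course mainly reaches those who stayed.

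If the answers of those who left are not sought, two of the three hypotheses rest largely on the more favourable part of the cohort. With the denominator also unstated, whether a majority improved could depend on a choice made after the data are seen.

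**Working it through.** **The plan's own figure.** The only powered quantity is the TUG. Inputs, all from Section II.a: "Total Number of Subjects: 30"; an SD of 5.8 s for the TUG; a pre-post correlation of 0.5 with a significance level of 0.05; and the claim "With a sample size of 30, we will have 80% power to detect a change of 3 seconds in the TUG".

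- SD of change = 5.8 × √(2 × (1 − 0.5)) = 5.8 s.
- n = (SD of change × (z for two-sided 0.05 + z for 80% power) / 3)² = (5.8 × (1.960 + 0.842) / 3)² ≈ 29.3, rounded up to 30.

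The stated 30 reproduces, as do the other seven rows of the table under the same formula. There is no matching calculation for the PGIC or the acceptability questions, and no allowance for dropout. What follows is therefore counting over assumed numbers of absentees.

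**Hypothesis 2.** Let *a* be the number of the 30 who do not answer at 10 weeks, so *c* = 30 − *a* respond. The smallest respondent majority is *m* = floor(*c*/2) + 1. If every absentee is unimproved, the share of enrolled subjects improved is *m*/30. If every absentee is improved, it is (*m* + *a*)/30. A majority of all 30 needs 16 improved. The values *a* = 3, 6 and 9 (10%, 20% and 30%) are assumptions.

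| Absent | Respondents | Smallest respondent majority | Of 30, absentees unimproved | Of 30, absentees improved | Respondent share needed for 16/30 |
|---|---|---|---|---|---|
| 3 | 27 | 14/27 = 51.9% | 14/30 = 46.7% | 17/30 = 56.7% | 16/27 = 59.3% |
| 6 | 24 | 13/24 = 54.2% | 13/30 = 43.3% | 19/30 = 63.3% | 16/24 = 66.7% |
| 9 | 21 | 11/21 = 52.4% | 11/30 = 36.7% | 20/30 = 66.7% | 16/21 = 76.2% |

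Under the unimproved assumption, the conclusion changes only within a band: 14 or 15 improved respondents with 3 absent, 13 to 15 with 6 absent, and 11 to 15 with 9 absent. If absentees improve at the same rate as respondents, the respondent percentage has no expected bias.

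**The 'yes' part of Hypothesis 3.** No required proportion of 'yes' answers is clearly set, so there is no threshold to cross. The possible shift can still be shown. If every respondent says 'yes', the respondent figure is 100%, against 27/30 = 90% of enrolled with 3 absent and 24/30 = 80% with 6 absent, counting absentees as not 'yes'.

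**Would the plan's procedures reach those who stop?** The attendance log goes to the coordinator only after the last class (Section III, Intervention). Subject status and adherence are reviewed quarterly (Section III.b), an interval longer than the course. Forms are reviewed on an ongoing basis and staff are expected at classes, so an absence could well be noticed. But no step is attached to noticing it.

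**The case against.** A reader might infer that subjects who stop are never asked, or are excluded from the closing assessment. The documents do not say so. No text available restricts the session to current attenders, and the advance reminder goes to subjects without qualification. The session may also be held away from the dojo. The word 'only' in the PGIC entry may simply mean that a change scale is not given at baseline. This all stands. What the plan lacks is a way to obtain answers from those who do not come, and a reminder does not provide one.

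A reader might also infer that the percentages will be calculated among respondents. That is not stated either; the denominator is undefined.

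Hypothesis 3 is partly protected, because its attendance condition is recorded at every class over a fixed 20. Missed classes would lower that result if dropouts stay in the attendance summary, which the plan does not say. Hypothesis 2 has no such protection.

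The six-month call recovers something: a second PGIC and reasons for not continuing karate. It cannot supply a 10-week rating.

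Finally, absence may be due to travel or unrelated illness, the PGIC analysis is descriptive, and this is a single-arm pilot. These points limit the weight of the concern. They also argue against counting everyone not reached as a failure in the headline figure.

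**Conclusion.** The point holds as a gap in data collection and reporting. Under the plan as written, the 10-week PGIC and the 'yes' part of feasibility would rest mainly on subjects who reach the final session, and the plan does not say what its percentages are percentages of.

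The size cannot be known, because no dropout rate is given and the answers of absentees are unknown. In the worst case of all absentees unimproved, 3 absences of 30 are enough to separate a respondent majority (51.9%) from a minority of those enrolled (46.7%); with 6 absences the figures are 54.2% and 43.3%. The direction of bias is plausible but conditional on those who stop being less favourable. It is not established.

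Part of Section V (recruitment and consent) was not available to check, so this is not a claim that the trial has no withdrawal procedure. The improvement is inexpensive and should be made.

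**What to change.** 1. In Section III, under the post-intervention focus group, add that every enrolled subject who has stopped or misses the session is phoned within about a week of the cohort's final class and given the PGIC and the two acceptability questions. Phone numbers are already collected on the demographic form, and the PGIC is already planned by phone at six months.
2. In Section III.b, state that the PGIC and 'yes' proportions are given among those who answered, in person or by phone, with the number not reached. Beside them, add a sensitivity figure with all enrolled subjects as denominator and those not reached counted as not improved or not 'yes'.
3. Reconcile the PGIC entry's restriction to the post-intervention assessment with its repeat at the six-month call.

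The cost is a few three-question calls by existing staff and some added sentences. Some answers will be taken by phone rather than in person, a small difference of mode worth reporting. The reported percentages may come out slightly lower.
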